|--|--|

| | |
|------------------------------------|---|
| | 
 - Carbon footprint of the intervention or carbon-saving due to the intervention |
| Procedures and measurements | 
Objective 1: Improve the integrated management of sick children
 
In Phase 1, in each region, after a pilot period of 6 months to test all the e-tools, eligible HFs will be randomized (by Region and HF) to the intervention or control arm. Sick children will be enrolled over a period of 6 to 9 months.
 
Primary outcome measures: (i) For assessing clinical cure at Day 7, a simple questionnaire (asking if the child is still sick, was hospitalized secondarily, or died) will be administered to all caregivers by phone; (ii) For measuring antibiotics prescribed at initial consultation, the treatment data recorded in the tablets or PCs by HCWs throughout the study will be compared between intervention and control arms.
 
Secondary outcome measures: To determine the quality of the consultation made by CHWs, including the rational use of antimicrobials (antibiotics and antimalarials), two sources of data will be used and compared between intervention and control arms:
 
 - the final decision on referral, tests performed, final diagnoses retained and treatment prescribed will be recorded in the tablets or PCs by HCWs at initial consultations and re-attendance visits. - during a cross-sectional survey, observers in the consultation room will record key symptoms and signs assessed by HCWs, diagnostic tests requested, final decision on referral, final diagnoses retained and treatment prescribed. 
Control arm: In control PHC facilities, sick children will be assessed, diagnosed and treated as per routine protocols by clinicians. A similar but simplified tablet or PC application will also be used in control facilities, but only to record outcome measure related data using an electronic case report form. HCWs in control facilities will be offered the usual training and supervision proposed by the CHMT.
 
In Phase 2, all selected HFs in the two regions will receive the intervention. Indicators monitored over time and across geographical areas will be measured the same way as in Phase 1, except that clinical cure, secondary hospitalizations and deaths may or may not be assessed through a phone call or an automated SMS or call to caregivers using the same simple questionnaire.
 
Objective 2: Improve the algorithm and adapt it to spatiotemporal variations
 
The algorithm will be improved in terms of diagnostic and prognostic accuracy and adapted to local fluctuations in epidemiology, demography, geography and resource availability. These modifications will be designed and supervised by clinical experts, based on accumulated data captured during the study in real-time and analyzed, including by ML when necessary. All modifications will first be tested on retrospectively collected data. If these analyses confirm an expected positive impact, the change in the algorithm will be implemented and its impact will be monitored through the continuous analysis of data looking at the related outcome indicators. For major modifications in the algorithm, a formal randomized sub-study will be conducted to assess precisely the potential benefit (or harm) on clinical outcome or non-inferiority. HCWs attending a child who could potentially benefit from this modification will be informed about the change in the algorithm. Either the modified branch or the standard branch of the algorithm will then appear on the screen to guide the HCW's decisions. Antimicrobial prescriptions, clinical cure and other outcomes related to the expected impact will be assessed the same way as in Phase 1 and compared between children managed with the new and the standard version of ePOCT+. If the positive impact is confirmed by the sub-study, the new algorithm branch will be implemented for all relevant children in the relevant HFs. Minor modifications in the algorithm (e.g. adding a non-critical symptom such as myalgia, or a slight modification of threshold of a laboratory test) will be implemented without sub-study, but some outcome indicators may be monitored.
 
Objective 3: Enhance disease surveillance and outbreak detection
 
All data generated by ePOCT+ will be sent to a central sever based at IHI. Data will be visualized through the medAL-outbreak dashboard made available to district health authorities using the key indicators they will have chosen. To enhance disease
 |

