7 OUTCOME MEASURES AND INDICATORS

7.1 Outcome measures and indicators for Objective 1 (Improve the integrated management of sick children)

The primary aim of the cluster-randomized study is to concurrently evaluate whether the use of ePOCT+ for case management of sick children in primary care, compared to routine care:

- (i) results in less antibiotic prescriptions at initial consultation;
- (ii) is non-inferior in clinical outcomes at day 7.

Rationale for choosing the primary aim and related primary analysis:

The second-generation ePOCT CDSA showed potential as an antimicrobial stewardship intervention for managing febrile children aged 2 months to 5 years, in a controlled trial setting in health facilities conducted in Dar es Salaam in 2015-16. Management with ePOCT resulted in a drastic reduction in (unnecessary) antibiotic prescriptions while maintaining similar, or possibly achieving better clinical outcomes by day 7. The current study seeks to generate evidence that would be more generalizable to a wider Tanzanian population. It aims at assessing the effect of an intervention package including the i) extended CDSA, called ePOCT+, ii) training and iii) supervision, when implemented under conditions closer to those that would be encountered in routine practice. ePOCT+ is an expansion of ePOCT that includes content for managing a wider age group (1 day to 14 years) with more comprehensive medical concerns (any acute medical or surgical problem). To determine whether ePOCT+ is a successful antimicrobial stewardship intervention, a significant reduction (by at least 25%) in antibiotic use without a negative effect on patient outcomes needs to be demonstrated (Gillespie et al., 2018).

Co-primary outcome measures for the cluster randomized controlled study in Phase 1:

- (i) % of children cured at day 7 (according to caregivers contacted through a phone call or home visit) in the intervention group (ePOCT+) as compared to control group (routine care)
- (ii) % of children prescribed an antibiotic at initial consultation, as reported by HCWs, in the intervention group (ePOCT+) as compared to control group (routine care)

Main outcome indicators (monitored over time and across geographical areas in all HFs in Phase 2):

- % of children cured at day 7
- % of children prescribed an antibiotic at initial consultation

Secondary outcome measures (Phase 1) or indicators (Phase 2):

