- Primary referral is a decision of referring the child to hospital taken by the HCW at the initial consultation - Secondary referral is a decision of referring the child to hospital taken by the HCW during a re-attendance visit taking place from the day after initial consultation up to day 7 included.
- Primary hospitalization is an admission to a hospital ward taking place the same day as the initial consultation
- Secondary hospitalization is an admission to a hospital ward taking place from the day after initial consultation up to the phone call at day 7 included. A non-referred secondary hospitalization is a direct visit to hospital without a re-attendance visit the same day at a HF participating in the study.
- Antibiotic prescription is any oral, intramuscular or intravenous (but not topical) antibiotic prescribed by a HCW during the initial consultation or a re-attendance visit
- Antimalarial prescription is any oral, rectal, intramuscular or intravenous antimalarial prescribed by a HCW during the initial consultation or a re-attendance visit
- Febrile child is a child with a history of fever and/or a high temperature
- Malaria testing is a malaria RDT or microscopy ordered by a HCW during an outpatient visit
- Day 7 is a range of 6-14 days post initial consultation to allow for completion of home visit for children whose caregiver reports having no phone / no phone number.

Additional longitudinal analyses:

- Change in % of children prescribed an antibiotic over time
- Change in % of children with basic anthropometrics and clinical signs measured over time (intervention arm only)
- Change in % of consultations where ePOCT+ was used over time (intervention arm only)

7.2 Indicators for Objective 2: Improve the algorithm and adapt it to spatiotemporal variations

- Number of positive impact modifications in the algorithm identified by ML-based analyses
- Number of positive impact modifications tested through randomized sub-studies
- % of these positive impact modifications confirmed to be safe and useful by randomized sub-studies
- Number of modifications implemented by type of impact (better clinical cure, less severe clinical outcomes, less medicines or diagnostic tests needed, shorter consultation time...)

Definitions used for the indicators of objective 2

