8.1.2 Management of sick children during the initial consultation

In HFs with dedicated staff for triaging patients, sick children will first be assessed by this person using the triage module of ePOCT+ in the tablet. If the child requires urgent treatment, the triaging person will immediately inform the attending HCW(s), so that she or he can give priority to that child over others waiting to be seen. If not, the child will queue normally and be attended by the next available HCW. As part of triage, the vital signs will be measured (temperature, respiratory rate, weight and MUAC) as well as, if the child fulfils certain clinical criteria, oxygen saturation and cardiac rate using the pulse oximeter. If there are no dedicated triage staff, the triage module will be deactivated and vital signs will be measured during the consultation.

The attending HCW will either manage the child using the ePOCT+ algorithm (in intervention facilities) or as per routine (in control facilities). If the child needs to go to another room for laboratory investigations (rapid tests or other), the HCW will be able to suspend the ePOCT+ algorithm and data recording in the tablet and attend another child in the meantime, opening a parallel session in the tablet. When the child returns with the test results, the HCW will resume the ePOCT+ algorithm and data recording of that child and continue the consultation normally. At the end of the consultation, the HCW, in both intervention and control facilities, will be asked to enter the final decision on referral, tests performed, final diagnoses and treatments prescribed (see chapter 8.1.6 on outcomes measurements). After the consultation, this information will be synced to the server at IHI offices as soon as there is internet connectivity.

Figure 9: Flowchart of health facilities and patients included in Phases 1 and 2

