8.1.7 Measurement of primary and secondary outcomes

Data captured on the tablets used by health care workers during the consultation

During the pilot phase before Phase 1 begins, tablets will be provided to HCWs in both intervention and control HFs. In intervention HFs the tablets will contain the patient registration module followed by the ePOCT+ algorithm that will guide them throughout the consultation process. In control HFs, tablets will only collect the patient demographics (see **Appendix 1**).

To determine the percentage of children prescribed an antibiotic or an antimalarial, as well as to know the final decision on referral and final diagnoses retained by HCWs, four questions will appear on the screen at the end of the consultation process, i.e. once the clinician has gone through the entire algorithm in intervention HFs or just after the patient registration module in control HFs. HCWs will be asked to document the final decision regarding the need for referral, tests performed and the results, decision on the date of follow-up (if needed), final diagnoses and final treatments prescribed. For each

medicine prescribed, the dosage and duration of the treatment will also be recorded (see **Appendix 1**).

Data captured through phone calls or home visits (Phase 1) or automated phone calls or SMS (Phase 2) to caregivers

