Analyses will follow CONSORT guidelines (Schulz et al. 2010, Piaggio et al. 2012) and intention-to-treat (ITT) principles, that is including all participants as randomized. A flowchart will describe the inclusion and follow-up of participants by study arm. Baseline characteristics will be described by study arm with summary statistics such as median and interquartile range or number and percentage; no formal testing between arms will be performed (Pocock et al. 2002). Outcomes will be described by arm using summary statistics. For the non-inferiority comparison between ePOCT+ and the control arm for clinical cure, a CI approach will be used. A figure illustrating the CIs and the non-inferiority margin will be presented. Primary analyses for the non-inferiority comparison will be performed on both the per protocol and ITT sets (Committee for Proprietary Medicinal P 2001). If ePOCT+ is found to be non-inferior to the control in terms of clinical cure rate, then we will assess for superiority using the ITT set. If non-inferiority is established, we will test for significant differences in the co-primary outcome of antibiotic prescription rate. For this outcome, the percentage of patients receiving antibiotics at day 0 will be assessed using multi-level logistic regression model regression with the cluster included as a random effect. Binary secondary outcomes will be evaluated in the same way. All estimates will be reported with 95% confidence intervals (CI).

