Effect modification of the primary outcome of antibiotic prescription of the primary endpoints will be performed in groups of patients where the highest reduction in antibiotic prescription is expected, and areas of extension of the content of the algorithm compared to the version tested in the previous ePOCT study. Effect modification by sex, age groups (young infants ages 1 to 59 days, children aged 2 months to 5 years, and children aged 5 to 14 years), respiratory symptoms, fever without clinical source, gastrointestinal complaints (vomiting and diarrhea), skin problems, ear and throat problems, anemia, and malnutrition will be assessed by incorporating an interaction between arm and the respective variable, acknowledging that power will be low. All models will be adjusted for clustering and the stratification factors (Kahan et al. 2012). Primary analyses will be complete case; we may adjust for further baseline variables which are associated with missing outcome data (which is analogous to performing multiple imputation in the case of a single endpoint). Further details will be provided in the statistical analysis plan.

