5.2.3. Participants eligibility

A child is eligible for the medAL-mentor study if:

- they visit a HF included in the medAL-mentor study

AND

- they meet the following inclusion criteria and none of the following exclusion criteria:

Inclusion Criteria:

- Aged 1 day (24 hours) to 14 years (inclusive)
- Presenting for an acute medical or surgical condition

Exclusion Criteria:

[figure not shown]
- Presenting for scheduled consultation for a chronic disease (e.g. HIV, TB, NCD, malnutrition)
- Presenting for routine preventive care (e.g. growth monitoring, vitamin supplementation, deworming, vaccination).

Eligibility criteria will be assessed using the routine registry. For the primary outcome measure, all eligible participants will be included in the analysis.

For secondary and exploratory outcomes, whose measurement is based on ePOCT+ data, only participants managed with the tool will be included in the analysis. In addition, participants whose caregiver was unavailable, unable or unwilling to provide oral consent will be excluded from the analysis.

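### In Phase 1, antibiotic capture as described depends on completing ePOCT+ in intervention facilities but not in control facilities, which risks differential missingness in co-primary outcome (ii)

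*Protocol*

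**What the plan says.** Co-primary outcome (ii) in Protocol Section 7.1 is the percentage "of children prescribed an antibiotic at initial consultation, as reported by HCWs". The synopsis (Procedures and measurements) names its source: "the treatment data recorded in the tablets or PCs by HCWs throughout the study will be compared between intervention and control arms". Section 8.1.7 says the closing questions on referral, tests, diagnoses and treatment appear on the screen "once the clinician has gone through the entire algorithm in intervention HFs or just after the patient registration module in control HFs". Section 8.1.2 describes the timing more evenly: "At the end of the consultation, the HCW, in both intervention and control facilities, will be asked to enter the final decision on referral", followed by tests, diagnoses and treatments.

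Section 10.3 commits to "intention-to-treat (ITT) principles, that is including all participants as randomized". Later in the same section: "Primary analyses will be complete case", with optional adjustment for baseline variables related to missing outcomes.

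The protocol foresees that the tool will not always be used:
- Section 7.1 lists among its longitudinal analyses "Change in % of consultations where ePOCT+ was used over time (intervention arm only".
- Section 12.2 names reluctance of clinicians to use the tool as a project risk.
- The synopsis (Intervention) says that emergency cases are not managed with it.

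SAP Section 2.1, looking back on Phase 1, reports that uptake differed considerably between facilities but gives no percentage. For the later medAL-mentor study the primary antibiotic outcome comes from the routine registry, whether or not the tool was used (SAP Sections 4.2, 5.2.3 and 6.1.1): "For the primary outcome measure, all eligible participants will be included in the analysis".

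**The concern.** In the intervention arm the route from registration to an antibiotic record runs through the whole algorithm, in a consultation that Section 6.1 expects to average 15 minutes. In the control arm it is one step. If a clinician registers a child, leaves the algorithm and treats as usual, the text describes no other way for that child's prescription to reach the dataset. A complete-case analysis then omits the child, and whether a child is omitted is linked to use of the intervention itself. Adjusting for baseline variables does not reliably repair missingness that arises after randomization in this way.

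The intervention-arm rate would then describe children managed to the end with ePOCT+, set against registered control children. The protocol's premise is that tool-guided prescribing is far below routine prescribing (Section 1.6), so the likely bias favours ePOCT+ and grows with non-use. Secondary outcomes on malaria treatment, referral and diagnosis that rely on the same closing questions are exposed as well. Section 8.1.7 also plans day-7 contact for all children. The two co-primary outcomes could therefore rest on different intervention-arm populations, although Section 7.1 needs both to call the intervention a success.

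**Working it through.** No stated figure is in dispute here, so there is none to reproduce. The check is a sensitivity calculation.

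**Inputs**
- Control rate 70% and intervention rate 23%: preliminary Phase 1 results, SAP Section 2.1. Assumption: 23% applies to completed-algorithm consultations. The SAP does not say so.
- Success criterion: a reduction of at least 25% (Protocol Section 7.1), read as relative.
- *u*, the share of intervention children without a completed algorithm: not in the documents. Assumed range 10% to 40%.
- *q*, the antibiotic rate in those children: not in the documents. Main value 70% (the control rate). Range 40% to 95%, where 95% is the routine-care rate of the earlier ePOCT trial (Protocol Section 1.6).
- The control rate is held at 70%, as if unrecorded control children were prescribed like recorded ones.

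**Formula**

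All-children intervention rate = (1 − u) × 23% + u × q. The overstatement of the reduction is u × (q − 23%).

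**Results with q = 70%** (recorded reduction 70 − 23 = 47 points, or 47/70 = 67%)

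| u | All-children rate | Absolute reduction | Relative reduction |
|---|---|---|---|
| 10% | 0.9 × 23 + 0.1 × 70 = 27.7% | 42.3 points | 60% |
| 20% | 0.8 × 23 + 0.2 × 70 = 32.4% | 37.6 points | 54% |
| 30% | 0.7 × 23 + 0.3 × 70 = 37.1% | 32.9 points | 47% |
| 40% | 0.6 × 23 + 0.4 × 70 = 41.8% | 28.2 points | 40% |

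**Overstatement per 10% of non-use**
- q = 40%: 0.1 × (40 − 23) = 1.7 points
- q = 70%: 0.1 × (70 − 23) = 4.7 points
- q = 95%: 0.1 × (95 − 23) = 7.2 points

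**Limits with no assumption about q** (from 23% × (1 − u) to that value plus u)
- u = 10%: 20.7% to 30.7%
- u = 20%: 18.4% to 38.4%
- u = 30%: 16.1% to 46.1%
- u = 40%: 13.8% to 53.8%

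These limits lie on both sides of 23%. The effect is overstated if q exceeds 23% and understated if q is below it.

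**Non-use needed to miss the 25% criterion**

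The intervention rate would have to exceed 0.75 × 70 = 52.5%, a rise of 29.5 points over 23%.
- q = 70%: 29.5 / 47 = 63%
- q = 95%: 29.5 / 72 = 41%
- q = 100%, the extreme: 29.5 / 77 = 38%

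**The case against.** The strongest reply is that Section 8.1.7 describes where the questions appear and does not say they are locked. Section 6.1 lets clinicians move freely through the algorithm, Section 8.1.6 has overrides recorded in the tool, and Section 8.1.2 asks both arms for final data when the consultation ends. The forms in Appendix 1 are not in the supplied text, and neither is the separate Phase 1 SAP that SAP Section 5.2.1 mentions. This stands in part: early access to the questions is possible but nowhere stated. None of these provisions supplies a record for a registered child whose algorithm was never opened or was abandoned.

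A reader might infer that only the intervention arm loses children. The documents do not support that. Control staff can also leave a child off the tablet, and complete-case analysis drops those children as well. The risk is differential loss of unknown size.

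A reader might also infer that the reported effect is overstated. That is not established. If simple cases with few antibiotics are the ones skipped, the bias reverses. SAP Section 2.1 attaches the 23% to facilities using ePOCT+, without naming the data source. If it already counts consultations without the tool, the correction above does not apply.

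A second source does exist. Observers record treatments in 18 of the 40 facilities, 25 consultations each, 450 per survey (Section 3.4.1). This is a useful check that can be compared between arms, but against a planned 40,000 patients it cannot supply the missing outcomes. Monitoring (Section 11.5) includes one visit per facility soon after on-site training to check that the tool is used, and it does not create records either.

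**Conclusion.** The point holds as a risk of differential missingness in co-primary (ii). As Section 8.1.7 is written, capture follows completion of the intervention in one arm and registration in the other. Complete-case analysis of such data does not meet the intention-to-treat statement in Section 10.3. The bias probably favours ePOCT+, on the premise that children managed without the tool are prescribed antibiotics more often than those managed with it.

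The illustrative size is 4.7 points per 10% of non-use at a 70% rate, with 1.7 to 7.2 points for rates of 40% to 95%. It rests on two assumptions that the documents neither confirm nor exclude: the meaning of the 23% and prescribing in non-use children. What is at stake is mainly the size of the effect and the intention-to-treat claim. A reader might infer that the conclusion of reduced prescribing is itself unsafe, but the figures do not support this. At the control rate, missing the 25% criterion takes about 63% non-use, and the documents report no such level.

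**What to change.** 1. In Section 8.1.7, make the same short closing form (referral, tests, diagnoses, treatment) reachable from the registered patient in both arms, whether or not the algorithm was completed, with a flag for completed or not completed. If the application already allows this, say so.
2. In Section 10.3, define the analysis set for co-primary (ii) as all registered, consented children.
3. Report by arm the number of registered children without an antibiotic record.
4. Add a sensitivity analysis over a stated range of prescribing in children without a record, applied to both arms.

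The cost is a small application change, a few sentences in the plan and possibly a less favourable estimate. The SAP already cites preliminary Phase 1 results, so step 1 may come too late for Phase 1 data. Steps 2 to 4 need no new collection, although without step 1 the children lacking a record can enter only through assumed values.

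A register-based comparison is optional. The medAL-mentor study covers the 20 former control facilities and 20 new ones (SAP Section 3.3), so the Phase 1 intervention facilities would need new abstraction. Protocol Section 1.4 describes the registers as often incomplete. Section 5.1 has electronic data erased where consent is absent, so counting all eligible children from registers would need its own consent provisions.
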